## **A Introduction**

### **A1 Study Abstract**

Non-infectious inflammatory eye disease, such as uveitis, is a chronic, auto-immune process that can occur in isolation or in the context of a systemic auto-immune condition. While corticosteroids are effective therapies, the side-effects of chronic steroid use require us to develop effective steroid-sparing therapies. There is only one FDA-approved steroid-sparing therapy for uveitis.

Tofacitinib is a small molecule that inhibits the signaling pathways of multiple inflammatory cytokines. It is already FDA-approved for the treatment of rheumatoid arthritis, psoriatic arthritis, and ulcerative colitis. It is routinely prescribed by practicing rheumatologists at Washington University for diseases that place patients at risk for long-term disability.

We have successfully treated a patient with refractory uveitis with off-label use of tofacitinib after failure with multiple conventional steroid-sparing therapies ([name] *et al. in submission*). We plan to evaluate whether tofacitinib may have efficacy in a larger series of cases.

### **A2 Primary Hypothesis**

Treatment with tofacitinib will limit ocular inflammation in the after steroids have been tapered off.

### **A3 Purpose of the Study Protocol**

To evaluate whether tofacitinib has clinical efficacy as a steroid-sparing agent for patients with uveitis.

---

## **B Background**

### **B1 Prior Literature and Studies**

There are several lines of evidence to suggest that tofacitinib would be an effective agent in ocular inflammatory disease. For example, inflammatory cytokines that activate JAK/STAT signaling have been implicated in the pathogenesis of inflammatory eye disease (1-3). Furthermore, inhibitors of IL-2 (4, 5) and IL-6 (6), which activate JAK/STAT signaling, have had clinical efficacy in small studies of inflammatory eye disease. Tofacitinib has also been used topically to treat a mouse model of ocular inflammation (7). Additionally, tofacitinib has demonstrated clinical efficacy in rheumatoid arthritis, psoriatic arthritis, and ulcerative colitis (8-11), which are associated with inflammatory eye disease. Thus, treatment of these patients with tofacitinib may trigger resolution of ocular inflammation by resolving the underlying systemic inflammatory disorder. Finally, reduced penetration of the blood-aqueous barrier may limit the efficacy of certain targeted therapies, such as etanercept and other biologic DMARDs. In contrast, a small molecule such as tofacitinib is likely to more efficiently cross of the blood-aqueous barrier.

---

## **B2 Rationale for this Study**

Non-infectious inflammatory ocular disease is an auto-immune condition of unknown etiology. Although uveitis often responds adequately to corticosteroids, there are many patients for which this treatment is either inadequate or not tolerated. In addition, chronic steroid use leads to significant morbidity. We propose an open-label trial of tofacitinib for patients with non-infectious inflammatory eye disease.

A patient with inadequate response to treatment would manifest with uveitis activity by slit lamp examination determination of anterior chamber cellularity, vitreous haze or new lesions of the retina / choroid. Persistent inflammation can manifest as ocular hypertension (greater than 21 mmHg measured by tonometry), complicating chronic topical corticosteroid administration, leading to glaucoma and permanent visual loss or perforation of the eye (which also can lead to permanent visual loss). Moreover, systemic corticosteroids may be required at a dose unsafe for chronic administration. In these situations, an immunosuppressive medication is often added as a "steroid-sparing" agent. If and when there is clinical response to the added immunosuppressive, the oral and/or topical corticosteroid dose can be reduced or eliminated to avoid toxicity.

There is currently only one FDA-approved steroid-sparing therapy (adalimumab) for the treatment of uveitis. Furthermore, adalimumab is effective in only 40-60% of cases of uveitis (12, 13). As a result, additional steroid-sparing therapies are needed for these vision-threatening diseases.

## **C Study Objectives**

### **C1 Primary Aim**

The primary endpoint will be treatment failure at week 24:

Treatment failure will be defined as

- Before or at week 8 (any one of the following criteria)
  - new inflammatory lesions relative to baseline
  - anterior chamber cell or vitreous haze > 0.5+ on SUN scale
  - worsening of visual acuity by two or more rows on ETDRS (Early Treatment of Diabetic Retinopathy Study) chart
- After week 8 (any one of the following criteria)
  - new inflammatory lesions relative to baseline
  - 2-step increase in anterior chamber cell or vitreous haze
  - worsening of visual acuity by two or more rows on ETDRS chart

Grade '0' will denote zero cells present per high power field or no vitreous haze and a change of full number grade will represent a "step change" (e.g. a change from grade 1 to 0 is considered a 1-step change).

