### **C2 Exploratory Analysis**

1. Treatment Failure According to Reason for Failure

- 
- anterior chamber cell
  - vitreous haze
  - new retinal lesions
  - worsening of best corrected visual acuity
2. Time to Treatment Failure
  3. Cystoid Macular Edema
    - change of cystoid macular edema based on optical coherence tomography
  4. Intraocular Pressure:
    - change in intraocular pressure as measured in mmHg during clinical evaluation
  5. Improvement Visual acuity (best-corrected ETDRS chart-measured acuities)
    - a clinically significant change in visual acuity will be defined as an improvement by 2 lines in the ETDRS chart.
  6. Angiography
    - Angiography will be assessed for clinically relevant patients (e.g. posterior or pan uveitis)
  7. Cataract
    - Patients will be assessed for cataract formation

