### **C3 Rationale for the Selection of Outcome Measures**

Outcome measures for uveitis are based on previously published phase 3 trials for steroid-sparing agents in inflammatory eye-disease (12, 13). Measurement of intraocular pressure, cataract formation, cystoid macular edema and visual acuity are important to determine the improvement or worsening of secondary effects of active inflammatory disease.

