## **E Study Design**

### **E1 Overview or Design Summary**

This study is a prospective, single-site, open-label investigation of tofacitinib for refractory uveitis. The study will be for 24 weeks, with potential 1-year extension for treatment responders. The patients will self-administer the medication.

Eligible patients would be those patients with a diagnosis of uveitis who meet the following criteria:

- 1) Disease sufficiently severe to require treatment with systemic corticosteroids, and
- 2) Referred from Ophthalmology to Rheumatology or Uveitis specialist for a steroid-sparing agent

For patients naive to oral steroid-sparing therapy (e.g., methotrexate, azathioprine, or mycophenolate), tofacitinib will be initiated as monotherapy. For patients who have failed or had only a partial response to oral steroid-sparing therapy, tofacitinib will be initiated as an add-on therapy. For patients intolerant to a conventional agent, tofacitinib will be initiated as replacement monotherapy. For patients who have failed biologic therapy (e.g. adalimumab), biologic therapy will be discontinued and tofacitinib will be initiated as replacement therapy without change to concurrent conventional steroid-sparing agents. Study visits will occur at baseline/enrollment, and weeks 4, 8, 12, 16, & 24 (+/- 2 weeks). Clinic visits may occur more frequently as determined by the treating physician. Laboratory monitoring (Table 1) will be obtained according to standard of care for drug toxicity monitoring. Clinical responses will be evaluated at 24 weeks, with the primary outcome defined as treatment failure.

All patients will undergo a predetermined oral steroid taper starting at 60mg of prednisone (or equivalent) and tapering over 14 weeks (Table 2). All patients will undergo a predetermined topical steroid drop taper starting at their current dose (Table 3).

Patients will have an ophthalmological evaluation by their treating ophthalmologist at Washington University. Steroid sparing therapy will be managed by rheumatologists or uveitis specialists at Washington University. All patients will be evaluated for an associated systemic rheumatologic condition.

---

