### **2.b Ethical Considerations**

There is one FDA-approved steroid-sparing therapy for uveitis (adalimumab). Tofacitinib and adalimumab are equally effective in treating the associated systemic disorder, psoriatic arthritis. For patients who have failed adalimumab, tofacitinib offers a reasonable alternative therapy.

Patients will have regular follow-up with both Ophthalmology and Rheumatology to monitor disease activity. Treatment with corticosteroids will be available for rescue therapy for all patients with uncontrolled disease.

Patients may be influenced to participate because an authority figure (their physician) may propose the study, however, steps that will be taken by the research team to minimize the possibility of coercion or undue influence during the consent process. The consent process will include full study disclosure, giving the patient a reasonable amount

---

of time to decide regarding participation and the opportunity to discuss with family and friends, and assuring the patient that they will receive the same quality of care regardless of study participation.

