### **3.f Prior and Concomitant Therapy**

All patients will be prescribed steroids with a uniform and pre-determined taper starting at prednisone 60mg daily (or equivalent) and tapering over 14 weeks to off.

Patients intolerant to an initial steroid-sparing therapy (e.g. methotrexate, azathioprine, or mycophenolate) will be started on tofacitinib and their prior steroid-sparing therapy will be discontinued. No other steroid sparing therapy will be initiated during the study period to avoid confounding of clinical efficacy.

Patients tolerant to prior steroid sparing therapy but with an incomplete control of their disease will have tofacitinib added to their steroid-sparing therapy. No other steroid sparing therapy will be initiated during the study period to avoid confounding of clinical efficacy.

Concomitant therapy with biologic steroid-sparing therapy such as adalimumab is prohibited due to the risk of infection.

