### **G3 Analysis Plan**

All analysis will be descriptive. We expect 40-60% of patients to meet the primary endpoint in each arm similar to adalimumab in the treatment of noninfectious uveitis. This is in contrast to the placebo arm, which had a treatment failure rate of 80% at 24 weeks (12).

Patients will be analyzed by intent to treat when all 5 patients in a treatment arm have either completed 6 months of therapy or discontinued therapy due to study withdrawal or indications for treatment cessation.

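### The primary endpoint in C1 has no corticosteroid criterion, so a patient given rescue steroid above the taper after week 8 could count as a non-failure

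*Combined protocol and SAP*

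**What the plan says.** **Endpoint.** C1 is a week-24 composite. Up to week 8 a patient fails with a new lesion, with "anterior chamber cell or vitreous haze > 0.5+ on SUN scale", or with a loss of two or more ETDRS rows. After week 8 the lesion and acuity items stay, and the grade item becomes a "2-step increase in anterior chamber cell or vitreous haze". C1 counts a step as one full number grade. The exploratory item "Treatment Failure According to Reason for Failure" in C2 has four entries: anterior chamber cell, vitreous haze, retinal lesions and acuity. Steroid use is not among them.

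**Steroid rules.** Section 3.f puts every patient on a "uniform and pre-determined taper starting at prednisone 60mg daily (or equivalent) and tapering over 14 weeks to off". For drops, E1 states: "All patients will undergo a predetermined topical steroid drop taper starting at their current dose". Section 2.b adds: "Treatment with corticosteroids will be available for rescue therapy for all patients with uncontrolled disease".

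**Aim and context.** A2 is about limiting inflammation once steroids are off, and A3 is about efficacy as a steroid-sparing agent. C3 says: "Outcome measures for uveitis are based on previously published phase 3 trials". G3 expects 40-60% of patients to meet the endpoint and then says: "This is in contrast to the placebo arm, which had a treatment failure rate of 80% at 24 weeks".

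**The concern.** The plan regulates steroid through two fixed tapers, permits rescue outside them, and then measures an outcome that takes no account of steroid. The threshold for failure also loosens after week 8, from an absolute limit to a two-step rise. A clinician may reasonably treat a flare that falls short of two steps.

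If that happens, an eye that is quiet because prednisone was restarted is grouped with an eye that is quiet on tofacitinib with steroids off. Only the second supports the hypothesis. The error runs one way: under C1 as written, rescue can hide a failure of steroid-sparing but cannot create one. The failure proportion is the study's main result, and G3 sets it beside an outside placebo rate, so its meaning should be fixed before the data are seen.

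**Working it through.** The plan gives no power calculation or derived figure to reproduce: the sample is at most 5 (G1) and the analysis is descriptive (G3, G4). The check is therefore a reading of the rules, followed by simple proportions.

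**1. Does any section score rescue steroid?**
- C1 and C2: no steroid item.
- 2.b: permits rescue; no definition of the trigger, no dose, no link to C1.
- 2.e: the response to failure is to stop tofacitinib and switch agent; rescue steroid is not mentioned.
- 2.i: cessation depends on C1 failure, not on rescue.
- 3.f: bars new steroid-sparing agents and concomitant biologics; says nothing on steroid above the taper.
- G3: intent to treat, so a rescued patient stays in the analysis.
- G5: covers missing outcomes only.

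None of them scores it.

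**2. Can a treated flare escape C1 after week 8?** C1 does not name the reference visit for the two-step rise, so take any reference grade r. The rise to 1+ is 1 − r full grades:

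| r | 0 | 0.5 | 1 | 2 |
|---|---|---|---|---|
| 1 − r | 1 | 0.5 | 0 | −1 |

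Every value is below 2, so 1+ is never a two-step rise. It does exceed the 0.5+ limit that means failure up to week 8.

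A rise to 2+ can escape as well. From a reference of 0.5+ it is 2 − 0.5 = 1.5 full grades, below 2. If the reference is a baseline of 2+, only 2 + 2 = 4+ would qualify.

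**3. What would the steroid record show?** Table 2 schedules 10 mg at week 8, 3 mg at week 12, and 0 at weeks 16 and 24. Without rescue, the oral dose at the last two nominal visits should be 0. Weeks 16 and 24 are 8 weeks apart. With the ±2-week windows the gap runs from 22 − 18 = 4 to 26 − 14 = 12 weeks. A short course could fall between the two visits and not appear in visit-day doses.

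**4. Size.** One reclassified patient moves the failure proportion by 1/n:
- n = 5: 1/5 = 20 points
- n = 4: 1/4 = 25 points
- n = 3: 1/3 = 33 points

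The smaller denominators can arise because G5 censors missing outcomes. Illustration with 5 analysed and 2 failures under C1, using exact (Clopper-Pearson) 95% intervals:

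| Rescued non-failures counted as failures | Proportion | 95% interval |
|---|---|---|
| 0 | 2/5 = 40% | 5-85% |
| 1 | 3/5 = 60% | 15-95% |
| 2 | 4/5 = 80% | 28-99% |

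**5. How likely is at least one such patient?** The documents give no rate. For an assumed per-patient chance q, independent across 5 patients, the probability is 1 − (1 − q)^5. For q = 5%, 10%, 20% and 30% this gives 23%, 41%, 67% and 83%.

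**The case against.** **Uncontrolled may mean failed.** The rescue sentence sits under Ethical Considerations and reads as a patient-protection statement, not a dosing rule. If it is meant for patients who already meet C1, rescue follows failure and the gap closes. This is a fair reading, but no section states it.

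**A grade of 1+ is not active disease.** The inclusion criteria define active disease as cell or haze of 2+ or more, or an active lesion. On that standard a patient at 1+ should not need rescue, and a rise from 0 to 2+ is a C1 failure if grade 0 is the reference. This weakens the 0 to 1+ example but does not remove the gap. A rise from 0.5+ to 2+ is active disease by the same definition, yet is only 1.5 grades.

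**Extra steroid is a departure from the taper.** Perhaps so, but 2.b permits it, no rule scores it, and intent to treat keeps the patient in.

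**The published comparison may be harmed.** C3 ties the endpoint to earlier trials, and the documents do not say how those trials scored rescue. This stands as a caution against changing C1 itself. It does not count against reporting a second proportion.

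**It is a descriptive pilot.** Any change of classification moves a 5-patient proportion by 20 points, the intervals overlap heavily, and no decision depends on a test. This stands, and it limits the weight of the point.

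**The data are already available.** F3 and F4 collect steroid dose under concomitant medication, H1 draws on the whole medical record, E1 allows extra visits, and I1 has weekly review. This largely answers any worry about data capture. It leaves the scoring question open.

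**Conclusion.** The concern holds. Applied exactly, C1 can record a patient as a week-24 non-failure after steroid was restarted or raised above the taper, which is not the steroid-sparing effect that A2 and A3 set out to show. Any resulting error favours the drug. Each case is worth 20 points with 5 patients analysed, and 25 or 33 points with 4 or 3.

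This rests on three conditions: that the rescue provision is not confined to patients who already meet C1, that at least one patient is rescued after week 8 for a rise of less than two steps, and that the patient has no new lesion or two-row acuity loss. How often this would happen cannot be judged from the documents. The shift is descriptive only and lies well within the sampling uncertainty. The point should be fixed, but it does not undermine the study as a pilot.

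**What to change.** Choose one before the data are reviewed:

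1. Add to C1 that starting or increasing corticosteroid above the schedule in Tables 2 and 3 for ocular inflammation is treatment failure, and add this to the list of reasons in C2.
2. Keep C1 as it is, and also report the failure proportion with rescued patients counted as failures.

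Option 2 is the safer choice if comparison with the cited trials is the priority. If rescue is meant only for patients who already meet C1, one sentence in 2.b saying so closes the gap.

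Under either option, list each patient's oral and topical steroid dose beside the week-24 outcome. Take the start date and indication of any rescue course, including local steroid, from the medical record that H1 already covers.

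The cost is one line in C1 or one extra proportion, plus a listing column. Topical and systemic doses are already collected at every visit. The reported failure proportion may look less favourable, and option 1 may affect comparability with the published trials.

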### **C2 Exploratory Analysis**

1. Treatment Failure According to Reason for Failure

- 
- anterior chamber cell
  - vitreous haze
  - new retinal lesions
  - worsening of best corrected visual acuity
2. Time to Treatment Failure
  3. Cystoid Macular Edema
    - change of cystoid macular edema based on optical coherence tomography
  4. Intraocular Pressure:
    - change in intraocular pressure as measured in mmHg during clinical evaluation
  5. Improvement Visual acuity (best-corrected ETDRS chart-measured acuities)
    - a clinically significant change in visual acuity will be defined as an improvement by 2 lines in the ETDRS chart.
  6. Angiography
    - Angiography will be assessed for clinically relevant patients (e.g. posterior or pan uveitis)
  7. Cataract
    - Patients will be assessed for cataract formation

### **C3 Rationale for the Selection of Outcome Measures**

Outcome measures for uveitis are based on previously published phase 3 trials for steroid-sparing agents in inflammatory eye-disease (12, 13). Measurement of intraocular pressure, cataract formation, cystoid macular edema and visual acuity are important to determine the improvement or worsening of secondary effects of active inflammatory disease.

## **D Investigational Agent**

### **D1 Preclinical Data**

Tofacitinib is a small molecule that reversibly inhibits Janus associated kinases (JAKs) with some selectivity for JAK1 and JAK3 (14). JAKs execute cytokine receptor signaling by phosphorylation and activation of signal transducers and activator of transcription (STAT) proteins, which subsequently dimerize, enter the cell nucleus, and initiate transcription of numerous inflammatory genes. Topical administration of tofacitinib has demonstrated efficacy in treating ocular inflammation in animal models (7).

### **D2 Clinical Data to Date**

We successfully treated one patient with off-label use of tofacitinib for refractory uveitis ([name] *et al. in submission*). Tofacitinib is also clinically efficacious and FDA-approved for the associated systemic rheumatologic diseases, rheumatoid arthritis and psoriatic arthritis, which are associated with inflammatory eye disease (8-10). Treatment with tofacitinib leads to a clinical response starting at 4-8 weeks after initiation of therapy (8-10). Administration of tofacitinib is approved for 5mg twice daily or 11mg extended release for rheumatoid arthritis. This dose has been in clinical practice since its FDA approval in 2012 with 19,406 patient-years of accumulated safety data.

---

### **D3 Dose Rationale and Risk/Benefits**

The planned use of this product uses the FDA-approved dose and route of administration for rheumatoid arthritis. Tofacitinib has more than 8 years of safety data from clinical trials and clinical use (15, 16). The risk of this medication is equivalent to the single FDA-approved steroid-sparing agent for uveitis, adalimumab (8, 10, 12, 13, 15, 17). Notable risks include infection, reactivation of tuberculosis and the development of malignancy. Benefits of tofacitinib included the protection of organs and tissues from autoimmune or inflammatory disease without the requirement for steroids.

## **E Study Design**

### **E1 Overview or Design Summary**

This study is a prospective, single-site, open-label investigation of tofacitinib for refractory uveitis. The study will be for 24 weeks, with potential 1-year extension for treatment responders. The patients will self-administer the medication.

Eligible patients would be those patients with a diagnosis of uveitis who meet the following criteria:

- 1) Disease sufficiently severe to require treatment with systemic corticosteroids, and
- 2) Referred from Ophthalmology to Rheumatology or Uveitis specialist for a steroid-sparing agent

For patients naive to oral steroid-sparing therapy (e.g., methotrexate, azathioprine, or mycophenolate), tofacitinib will be initiated as monotherapy. For patients who have failed or had only a partial response to oral steroid-sparing therapy, tofacitinib will be initiated as an add-on therapy. For patients intolerant to a conventional agent, tofacitinib will be initiated as replacement monotherapy. For patients who have failed biologic therapy (e.g. adalimumab), biologic therapy will be discontinued and tofacitinib will be initiated as replacement therapy without change to concurrent conventional steroid-sparing agents. Study visits will occur at baseline/enrollment, and weeks 4, 8, 12, 16, & 24 (+/- 2 weeks). Clinic visits may occur more frequently as determined by the treating physician. Laboratory monitoring (Table 1) will be obtained according to standard of care for drug toxicity monitoring. Clinical responses will be evaluated at 24 weeks, with the primary outcome defined as treatment failure.

All patients will undergo a predetermined oral steroid taper starting at 60mg of prednisone (or equivalent) and tapering over 14 weeks (Table 2). All patients will undergo a predetermined topical steroid drop taper starting at their current dose (Table 3).

Patients will have an ophthalmological evaluation by their treating ophthalmologist at Washington University. Steroid sparing therapy will be managed by rheumatologists or uveitis specialists at Washington University. All patients will be evaluated for an associated systemic rheumatologic condition.

---

